- e Only subjects that meet all eligibility criteria will undergo the Screening MRI
- f Investigator will aspirate synovial fluid prior to knee injection when possible (physician's discretion). Collected synovial fluid will be sent to MC3M for testing (details in study manuals).
- g PTT may be ordered if deemed appropriate by the treating investigator
- h CBC should include a platelet count
- i Basic metabolic panel and Liver function panel may be substituted for a Comprehensive metabolic panel (physician's discretion) as long as the test includes an ALT and Total Bilirubin
- j Assessments completed during an Unscheduled Visit will be at the discretion of the treating investigator based on the reason for visit and examination of the subject. Laboratory assessments may be ordered at the discretion of the treating investigator.
- k Observation of the harvest site will be completed at the 7-day follow-up and 30-day follow-up visits. This will only be done for subjects on Arm 1 and Arm 2.
- l Please refer to the Operations Manual for specific results required for this testing
- m End of study visit: Assessments required will be at the discretion of the treating investigator in order to ensure subject safety. The EOS visit would only occur in the event the study is discontinued early (see Section 7.5)
- n Optional, at the discretion of the treating investigator
- o Refer to the Operations Manual for Arm-specific product release criteria requirements.
- p Treating Investigator must complete the Pre-Treatment Confirmation of Subject Eligibility form PRIOR to procedure or UCT dispensing.
- q Only subjects randomized to Arm 1 or Arm 2.
- r Only subject randomized to receive the CSI treatment in any of the 3 arms.

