### **4.3 Enrollment**

Subjects will be enrolled after the investigator has completed the following: confirm the subject has signed the informed consent and Health Insurance Portability and Accountability Act (HIPAA) Authorization, all screening assessments have been completed, and confirm that the subject has met all the inclusion criteria and none of the exclusion criteria.

Randomization can occur at any time after confirmation that the subject meets eligibility, but should occur within 30 days of the date of informed consent form signing. If the period is more than 30 days, an updated informed consent process must take place.

Enrollment of subjects is expected to last approximately 13 months in order to obtain the numbers needed. An additional three months has been incorporated into the study to allow for unanticipated delays and potential protocol changes.

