### **4.5 Study Stopping Rules**

If one of the following safety issues occurs, further enrollment will be halted until the Medical Monitor, [name], reviews all available data and makes recommendations as to the next steps:

- Any potential related serious adverse event (SAE).
- Other findings that, at the discretion of the study team, DSMB, investigator and/or Medical Monitor, indicate that the study should be halted.

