#### **8.1 Study Visit Assessments**

##### **8.1.1 Screening Visit (Visit 1)**

- Administer informed consent and HIPAA Authorization
- Collect demography
- Collect medical and surgical history
- Collect prior and concomitant medications
- Collect Knee Osteoarthritis History
- Review inclusion and exclusion criteria
- Focused knee assessment
- Perform vital signs
- Knee MRI (only if the subject is eligible for the study)
- Collect subject PROs
- Perform pregnancy test (on female subjects of childbearing potential)
- Blood Collection (safety labs)
- Once all screening assessments are complete and eligibility has been confirmed by the treating investigator, the subject may be randomized.
- Schedule the subject for the appropriate Treatment Visit procedure based on randomization

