### 9.4.3 Continuous Monitoring of Specific Adverse Events

In addition, the incidence of specific safety related events of concern will be continuously monitored separately in each treatment arm at each center throughout the study to determine if any of their observed subject-based incidence rates exceed a threshold incidence rate of concern pre-specified for each particular event (for example infection and allergic reaction related to study harvest procedure and/or knee injection).

These rules will be implemented by Advanced Clinical continuously monitoring the occurrence of any events to determine if the currently observed rate of each exceeds the corresponding threshold rate of concern with a pre-specified level of confidence. The stopping rule will be considered to be met if the lower 95% confidence limit on the observed incidence rate exceeds the corresponding threshold level of concern for that event. If any stopping rule is met, enrollment and randomization will be suspended pending expedited DSMB review.

The following table describes the minimum number of events out of the selected numbers of subjects randomized to each treatment arm at each site

which, if equaled or exceeded, would satisfy the stopping rule for each event of concern.

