**Table 1. Study Termination Rules for Infection and Allergic Reaction:**

Minimum Number of Subjects with Events Meeting Stopping Rule for Infection and Allergic Reaction (infections and/or allergic reactions must be related to the harvesting procedure and/or knee injection) for Selected Numbers of Subjects Randomized Per Treatment Arm at each Center Using a Threshold Incidence Rate of Concern of 10%

Number of Subjects with Event	Number of Randomized Subjects Total	Incidence Rate	Lower 95% Confidence Limit, Wilson score method
1	5	20%	4%
2	5	40%	12%
1	10	10%	2%
2	10	20%	6%
3	10	30%	11%
4	10	40%	17%
4	20	20%	8%
5	20	25%	11%
6	20	30%	15%
5	30	17%	7%
6	30	20%	10%
7	30	23%	12%

Examples above illustrate threshold number of events that exceed the stopping rule (highlighted in bold); non-highlighted entries illustrate the observed incidence rate and the lower 95% confidence limit that does not exceed the stopping rule threshold of 10%

For each treatment arm at each center: if the lower confidence interval for the estimated infection and allergic reaction rate is 10% or higher, then enrollment and randomization will be suspended pending DSMB review. Infection and/or allergic reactions must be related to the harvesting procedure and/or knee injection.

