### **10.8 Medical Monitor and Data Safety Monitoring Board (DSMB)**

All adverse events will be recorded on the adverse event forms, and the treatment related SAEs will be sent to the IRB, per their reporting requirements, and to sponsor. The study medical monitor or designee will review all adverse event reports. Further details are captured in the study medical monitoring plan, data management plan, and safety management plan created for this study by Advanced Clinical and maintained in the study Trial Master File.

The DSMB is responsible for monitoring the safety of the trial subjects, and data integrity during periodic and ad hoc reviews. The DSMB will meet every 6 months; it can recommend to the sponsor and the study executive committee the continuation of study as planned, modification of the protocol, or the stopping of the study.

The sponsor will ensure the timely communication of the safety and efficacy data to the DSMB according to the agreed upon schedules or within reasonable time if requested for

an ad hoc analysis. The DSMB will meet bi-annually and ad hoc as specified in its charter.

Data accrual will be performed continuously as the study is being performed. Advanced Clinical, LLC, is the CRO that is responsible for the data management plan and integrity of the study data. The study medical monitor will be working continuously with Advanced Clinical to assess the data in regard to safety concerns and will recommend ad hoc review by the DSMB as necessary.

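### The safety stopping rules halt enrollment and randomization but do not automatically hold harvest and injection for subjects already randomized and awaiting Day 0

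*Combined protocol and SAP*

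**What the plan says.** Three places state what happens when a safety rule is met.

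- Section 9.4.3, continuous monitoring: "If any stopping rule is met, enrollment and randomization will be suspended pending expedited DSMB review".
- The text under Table 1, for each treatment arm at each center: "then enrollment and randomization will be suspended pending DSMB review". Only infections and allergic reactions attributed to the harvest or the knee injection count.
- Section 4.5, triggered by any potentially related SAE: "further enrollment will be halted until the Medical Monitor" has reviewed the data. Its second trigger reads "Other findings that, at the discretion of the study team, DSMB, investigator and/or Medical Monitor, indicate that the study should be halted", but the stated action is the same halt to enrollment.

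The order of steps is set elsewhere. Section 4.3 defines enrollment by consent, completed screening and confirmed eligibility, and adds: "Randomization can occur at any time after confirmation that the subject meets eligibility". Section 8.1.1 places randomization at the Screening Visit and then tells the site: "Schedule the subject for the appropriate Treatment Visit procedure based on randomization". Harvest, cell preparation and injection are listed at a separate visit, Day 0 (8.1.2). The check required on that day is an eligibility check: "Treating Investigator must complete the Pre-Treatment Confirmation of Subject Eligibility form PRIOR to procedure or UCT dispensing" (1.3, footnote p).

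**The concern.** A stopping rule should interrupt exposure to the suspected hazard. Here the hazard is the Day 0 procedure, while the automatic action stops only the steps before it. A subject who was randomized last week and is booked for next week has passed every step that the rules suspend. If sites follow the text, that subject can undergo the procedure under review before the DSMB or Medical Monitor has reached a view.

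Section 4.5 is narrower than 9.4.3. It does not mention randomization, so as written an enrolled subject could still be randomized during the halt.

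**Working it through.** **The plan's own boundary.** Table 1 uses the two-sided 95% Wilson lower limit, [p + z²/2n − z√(p(1−p)/n + z²/4n²)] / (1 + z²/n), with z = 1.96. For 2 events in 5: (0.400 + 0.384 − 1.96 × √(0.0480 + 0.0384)) / 1.768 = 0.118, which matches the printed 12%. All twelve rows reproduce after rounding; 6 in 30 is 9.51%, printed as 10%. The trigger is as described. The question is what it stops.

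**Which steps each rule reaches.**

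| Step | 9.4.3 and Table 1 text | 4.5 |
|---|---|---|
| Enrollment | suspended | halted |
| Randomization | suspended | not mentioned |
| Day 0 harvest, UCT dispensing, injection | not mentioned | not mentioned |

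**Number affected.** Inputs from the documents:
- 480 subjects, 120 per center, 40 per Arm per center, split 30 MSC and 10 CSI (6.2.2). Each of the four treatment groups therefore has 30 subjects per center, the CSI group being 10 from each Arm.
- Enrollment of about 13 months plus a 3-month allowance (4.3).

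Assumptions, because the documents do not state them: even accrual, 7 to 30 days from randomization to Day 0, a review of 7 to 14 days, and a 30.4-day month.

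Daily rate = subjects / months / 30.4:

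| Unit | Subjects | 16 months | 13 months |
|---|---|---|---|
| Flagged group, one center | 30 | 0.0617 | 0.0759 |
| One Arm, one center | 40 | 0.0822 | 0.1012 |
| Whole center | 120 | 0.247 | 0.304 |
| Trial | 480 | 0.99 | 1.21 |

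For the flagged group at one center:
- Waiting = rate × lag: 0.0617 × 7 = 0.43 to 0.0759 × 30 = 2.28. With Poisson arrivals, the chance that nobody is waiting is exp(−0.43) = 0.65 at the low end and exp(−2.28) = 0.10 at the high end.
- Treated during the review = rate × min(lag, review): 0.0617 × 7 = 0.43 to 0.0759 × 14 = 1.06.
- Further events at a true rate of 10%, the threshold of concern: 0.43 × 0.10 = 0.04 to 1.06 × 0.10 = 0.11.
- Upper bound at 40%, the highest observed rate among the rows Table 1 marks as meeting the rule: 1.06 × 0.40 = 0.42.

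Under 4.5 the halt is trial-wide, so 0.99 to 1.21 Day 0 visits fall due per day of review, or 6.9 to 8.5 in 7 days.

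**The case against.** **The operational detail may sit elsewhere.** Section 9.5 refers to the DSMB charter, and 10.8 to medical monitoring and safety management plans. None was supplied, and any of them may contain a hold. This stands as a limit on the finding. It does not remove it: the protocol states the action in three places, none of which mentions pending procedures or points to a hold elsewhere.

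**Other safeguards exist.** The investigator may withdraw a subject for safety (7.1), the sponsor may discontinue the study (7.5), and the Medical Monitor "will recommend ad hoc review by the DSMB as necessary" (10.8). Subjects are to be told of relevant new information (8.2.1) and may leave at any time (7.2). A reader might infer that nothing can stop a Day 0 procedure during a review, or that the plan directs sites to carry on treating. The documents support neither reading. What is missing is an automatic temporary hold: withdrawal and discontinuation end participation, and information and withdrawal rights leave the decision to the subject.

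**The harm is small.** This is correct. A reader might apply the 20% to 40% rates in Table 1's qualifying rows to all 40 subjects in an Arm and expect up to 1.42 × 0.40 = 0.57 further events in a 14-day review. That overstates it. The rule is evaluated by treatment group, 30 per center, and rates observed when a boundary is crossed are selected for being high. The 10 CSI subjects in the Arm share the risk only if the harvest or injection itself is the cause, and Arm 3 has no harvest. Table 1 also sets no minimum severity, so the events need not be serious.

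**A hold has costs beyond rescheduling.** This also stands. PROs, MRI and safety labs before treatment are scheduled only at screening, so a hold ages the baseline of both co-primary endpoints.

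**Conclusion.** The gap is real on the text. The automatic actions in 9.4.3, under Table 1 and in 4.5 all fall before Day 0, and nothing in the supplied documents automatically holds a randomized, untreated subject from harvest and injection while the review is pending.

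Its expected size is small for a 9.4.3 trigger: about one subject or fewer treated during the review, often nobody waiting, and well under one further event. It is larger for 4.5, at about one Day 0 visit per day across the trial. These figures rest on the assumed lag, review length and even accrual, and the finding is conditional on what the charter and safety plans say. I rate it a minor to moderate safety clarification. The case rests on closing an avoidable exposure after an alarm, and not on a large expected number of events.

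**What to change.** **Section 9.4.3 and the sentence under Table 1.** Add: *and pending Day 0 harvest, UCT dispensing and injection procedures in the affected Arm(s) at the affected center (MSC and CSI subjects alike; all Arms at that center if the flagged group is CSI) will be held until the DSMB review is complete.* MSC and CSI subjects are held together because they share the harvest in Arms 1 and 2 and the injection in every Arm, and because holding one group alone could reveal assignment.

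**Section 4.5.** Restate the action as: *enrollment and randomization stop, and pending Day 0 procedures are held, until the Medical Monitor has completed the review of all available data; the Medical Monitor may release unaffected Arms or sites earlier, and the hold continues for the affected Arm(s) and site(s).* The last clause is needed so that an early release elsewhere cannot be read as ending the hold where the problem lies.

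**Held subjects.** They keep their assignment, eligibility is reconfirmed on the existing pre-treatment form, and PROs are repeated if the hold takes them past the 30-day screening window. Align the charter and the safety plan with this wording.

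**Cost.**
- Per 9.4.3 trigger with a 7 to 14 day review, delayed Day 0 visits number 0.0822 × 7 = 0.6 to 0.1012 × 14 = 1.4 for one Arm at one center, or 0.247 × 7 = 1.7 to 0.304 × 14 = 4.3 for a whole center if CSI is flagged.
- Under 4.5, about one visit per calendar day is delayed trial-wide until release, possibly after a single potentially related SAE.
- Some subjects may need a longer or repeated NSAID or antiplatelet interruption (5.1.2, items 12 and 15).
- Baseline PROs, labs and MRI will be slightly older.
- No sample size, endpoint or analysis changes.

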#### **8.2.16 Pregnancy Testing**

Pregnancy testing for human chorionic gonadotrophin (hCG) will be performed on female subjects of childbearing potential (refer to eligibility criteria). This may be done using a urine or serum sample. Pregnancy testing will be done at two time points:

- a) **Screening Visit**- if the test is positive the subject will be a screen failure.
- b) **Treatment Visit** (prior to procedure/knee injection)- if the test is positive, within 7 days of the Treatment Visit, the subject will be discontinued from the study.

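### The infection and allergic-reaction stopping rule counts procedure-related events but divides by subjects randomized, so it can require one event more than its 10% threshold intends

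*Combined protocol and SAP*

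**What the plan says.** Section 9.4.3 has the CRO monitor specified events continuously, separately for each treatment arm at each centre. If the lower 95% confidence limit for the incidence passes the threshold, enrolment and randomization are suspended pending DSMB review.

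- **Denominator.** The text leading into Table 1 reads: "The following table describes the minimum number of events out of the selected numbers of subjects randomized to each treatment arm at each site". The table's column header is "Number of Randomized Subjects Total".
- **Numerator.** The table title restricts the events: "infections and/or allergic reactions must be related to the harvesting procedure and/or knee injection". The note below the table repeats the restriction.
- **Method.** Table 1 gives the "Lower 95% Confidence Limit, Wilson score method" against a threshold of 10%.
- **Timing.** The Schedule of Activities (1.3) puts randomization in the screening column, headed -30 days, and the procedure and injection on Day 0. Section 8.1.1 ends the screening visit with: "Schedule the subject for the appropriate Treatment Visit procedure based on randomization".
- **Randomized but never treated.** Under 8.2.16, after a positive pregnancy test at the Treatment Visit, before the procedure, "the subject will be discontinued from the study". Section 7.2 allows withdrawal at any time.

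Section 9.4.2 names a safety population for the adverse event tables. The supplied text neither defines it nor applies it to this rule.

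**The concern.** The numerator and denominator describe different people. Someone who has been randomized but has had neither harvest nor injection cannot contribute an event related to either, yet still enlarges the denominator. The resulting error has one direction. It lowers the observed rate and its lower limit, so it can delay suspension and DSMB review but never bring them forward.

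The rule operates in small groups. Section 9.2 plans 30 subjects per treatment group per site, and Table 1 starts at 5. At these sizes the boundary is a step function of two to seven events, so one or two unexposed subjects can move the required count by a whole event.

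**Working it through.** **1. Reproducing Table 1.** The lower Wilson limit for x events in n subjects, with p = x/n and z = 1.96, is

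L = [p + z²/2n − z·√(p(1−p)/n + z²/4n²)] / (1 + z²/n).

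For 2/5: L = (0.4 + 0.3842 − 0.5762)/1.7683 = 0.118, printed as 12%. For 3/10: L = (0.3 + 0.1921 − 0.3429)/1.3842 = 0.108, printed as 11%. All 12 rows match to the whole percent. The plan does not say whether the limit is one- or two-sided; the two-sided 95% limit reproduces the table, whereas a one-sided 95% limit would give 14.3% for 2/5.

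The 6/30 row is 9.51% before rounding. It is bold only because it prints as 10%. Steps 2 and 4 therefore use two conventions: unrounded L above 10%, and L rounded to whole percent and at least 10%.

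**2. Minimum number of subjects with events that meets the rule**

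| Required count | n, unrounded | n, rounded as printed |
|---|---|---|
| 2 | 2–5 | 2–6 |
| 3 | 6–10 | 7–11 |
| 4 | 11–16 | 12–17 |
| 5 | 17–22 | 18–23 |
| 6 | 23–28 | 24–30 |
| 7 | 29–35 | 31–36 |

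**3. Same events, two denominators**

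| Events | Treated: L | Randomized: L |
|---|---|---|
| 2 | 5: 11.8%, met | 7: 8.2%, not met |
| 3 | 10: 10.8%, met | 12: 8.9%, not met |
| 4 | 16: 10.2%, met | 20: 8.1%, not met |

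These three contrasts hold under both conventions.

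**4. How often an extra event is needed.** The number untreated at a look is not in the documents, so 1 and 2 are assumed. Treated counts run from 5 up to a randomized total of 30.

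| Untreated | Unrounded: treated counts affected | Rounded: treated counts affected |
|---|---|---|
| 1 | 5 of 25 (5, 10, 16, 22, 28) | 4 of 25 (6, 11, 17, 23) |
| 2 | 9 of 24 (5, 9, 10, 15, 16, 21, 22, 27, 28) | 8 of 24 (5, 6, 10, 11, 16, 17, 22, 23) |

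The totals are close, but the affected sizes largely differ. With 28 treated and 2 untreated, the unrounded rule needs 7 events instead of 6. Under the printed 6/30 row there is no delay.

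**5. Is 1 or 2 plausible?** Planned accrual is 480 subjects in 13 months (4.3) over 4 treatment groups × 4 sites = 16 cells: 480/13/16 = 2.3 per cell per month. Over 16 months, using the three-month allowance, it is 1.9. At 2.3 per month, a 30-day lag leaves about 2.3 pending per cell and a 15-day lag about 1.2. The lag itself is an assumption.

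**6. Chance of meeting the rule at one look.** This is P(X ≥ required count) with X binomial over treated subjects.

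| Treated / randomized | True rate | Treated denominator | Randomized denominator |
|---|---|---|---|
| 5 / 7 | 30% | 47% (2 needed) | 16% (3 needed) |
| 10 / 12 | 30% | 62% (3 needed) | 35% (4 needed) |
| 16 / 20 | 20% | 40% (4 needed) | 20% (5 needed) |
| 16 / 20 | 30% | 75% (4 needed) | 55% (5 needed) |

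The 16/20 rows assume 4 untreated, more than step 5 suggests. All these rows are sizes at which the boundary does shift; at most sizes it does not.

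**The case against.** The strongest objection is that the plan has other protection. Section 4.5 halts enrolment for Medical Monitor review on any potentially related SAE, with no denominator, and allows a halt on other findings at the discretion of the study team, DSMB, investigator or Medical Monitor. Section 10.8 lets the Medical Monitor recommend ad hoc DSMB review. This stands: a serious related infection or allergic reaction does not wait for Table 1. What remains are non-serious events, for which section 4.5 offers only a discretionary halt.

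The gap is also unquantified and mostly transient. Pending subjects join the at-risk group once treated. Subjects in Arms 1 and 2 whose product fails acceptance have already had the harvest (6.0), so they belong in the denominator. A positive Day 0 pregnancy test should be uncommon at ages 40 to 70 after a negative screening test. This limits the size of the problem but does not remove the mismatch.

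A reader might infer that the denominator always contains unexposed subjects, or that the lag from randomization to treatment is unlimited. The documents support neither. A cell accruing about two subjects a month can have none pending, and the Schedule of Activities places screening, with randomization, at -30 days. The 30-day limit in 4.3 is a different interval, from consent to randomization.

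Finally, the SAP mentioned in 9.3, the DSMB charter or the safety management plan may specify the operating denominator. None is in the supplied text, and the text that is supplied consistently says randomized.

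**Conclusion.** The point holds as a mismatch between numerator and denominator that can make the rule trigger one event late. Its size is modest. With 1 or 2 subjects untreated, an extra event is needed at 4 or 5 of 25, or at 8 or 9 of 24, treated counts, depending on the rounding convention; most looks are unaffected. Where the boundary does shift, the chance of triggering at that look can fall substantially, for example from 62% to 35% with 10 treated of 12 randomized and a true rate of 30%.

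This rests on an assumed number untreated, on monitoring cells of up to 30 subjects as in 9.2 and Table 1, and on the rule being run as written. It does not show that serious events would be missed or that the rule is late at every look. It is also separate from whether 6/30 should count as meeting the rule.

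**What to change.** In section 9.4.3 and in the title and column header of Table 1, replace randomized subjects with subjects who have started the harvest procedure or received the knee injection, in that treatment arm at that centre. This wording keeps subjects who were harvested and then discontinued for product failure, who remain at risk of a harvest-related event. Leave the 10% threshold and the Wilson method unchanged.

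The cost is a wording change and an update to the CRO's monitoring program; the procedure and injection take place at the Day 0 visit, so exposure dates should be available. The downside is that the rule may trigger slightly earlier. At a true rate of exactly 10%, the chance of meeting it at one look with 10 treated of 12 randomized rises from 1.3% to 7.0%, which is what the 3/10 row gives when all 10 have been treated.
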